#### 9.9. Limitations of the Research Methods

As C4591079 utilizes data from C4591036, potential limitations are common to both studies and should be noted:

- Because of the decline in number of COMIRNATY-associated myocarditis cases (according to the Vaccines Adverse Events Reporting System [VAERS], cases reported in the US reached a peak in June 2021 and dropped dramatically after October 2021), the myocarditis/pericarditis cohort is largely comprised of retrospectively ascertained cases.
- Patients will be excluded from participation if plausible etiologies for myocarditis other than COMIRNATY-associated myocarditis are known at enrollment. It is possible that a plausible alternative etiology will be discovered only after a participant is enrolled. If so, those participants will be followed per C4591036 but will be accounted for separately in the statistical analysis.
- Some individuals who had COMIRNATY-associated myocarditis/pericarditis
  prior to the start of the study period may decline consent/assent or be difficult to
  reach. Each clinical center enrolling under C4591036 will work closely with
  pediatric offices to maximize return for scheduled visits. Participants who have
  returned to normal health and cardiac status may also be less inclined to return
  for follow-up at the recommended time points.
- A waiver of consent can be requested for collection of information related to clinical care when clinical sites are unable to reach participants with a history of vaccine myocarditis/pericarditis or COVID-19-related myocarditis/pericarditis, including MIS-C. In such patients, data collection will be limited to "retrospective" medical records review, including images obtained in the course of clinical care. No activities that are solely research-related are obtained or required.
- CMRIs are performed only when ordered as part of routine clinical care, and there may be practice variation among centers/providers regarding timing and protocols for cMRI.
- The COMIRNATY myocarditis and comparison participants are symptomatic
  patients evaluated and diagnosed in medical centers. They will not include
  individuals in the community with subclinical myocarditis/pericarditis. The study
  population will only include those with clinical myocarditis/pericarditis. Therefore,
  results from this study cannot be generalized to those in a subclinical
  myocarditis population.
- While the comparator cohort of persons <21 years of age with COVID-19associated myocarditis/pericarditis, including MIS-C, is the most relevant from a clinical standpoint in weighing the risks of vaccination vs. COVID-19-related myocardial injury, patients with COVID-19-associated myocarditis/pericarditis are less likely to have had a cMRI during the acute episode of

myocarditis/pericarditis due to practices in place to minimize the risks of COVID-19 exposures to hospital personnel. Compared to patients with COMIRNATY-associated myocarditis/pericarditis, they are expected to include a lower percentage of patients who are white, non-Hispanic, and male, and their age distribution will include children who are younger.

- We do not anticipate being able to separate Cohort 3 into COVID-19-associated myocarditis/pericarditis with or without MIS-C because of the rarity of myocardial involvement in children with acute severe COVID-19. The rarity of myocardial involvement in acute severe COVID-19 versus MIS-C may relate to the fact that children with myocardial involvement often meet the CDC's case definition for MIS-C.
- Although the study uses data from the US and Canada, given the expected diversity of study participants, the results of the study should be generalizable to the population in regions outside the United States. We will explore the association of race, ethnicity, and other sociodemographic factors with acute and long-term outcomes of myocarditis.
- The incidence of COVID-19 vaccine-associated myocarditis is changing over time. For example, the incidence of myocarditis associated with booster doses is much lower than that observed in the primary series. Moreover, vaccines themselves may be modified, and the background prevalence of prior COVID-19 in the population is increasing and may change susceptibility to vaccine-associated myocarditis. For these reasons, we may have limited power to determine differences in the natural history of outcomes of vaccine- associated myocarditis between different COVID-19 Pfizer-BioNTech vaccines.

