### 9.2.1. Inclusion Criteria

Data for this interim analysis are derived from the ongoing C4591036 study, "Low-interventional Study of Myocarditis and Pericarditis Associated with COMIRNATY in Persons Less Than 21 Years of Age." The following inclusion criteria are used for eligibility in the C4591036 study:

Patients must meet all of the following inclusion criteria to be eligible for inclusion in the study:

[figure not shown]
Cohort 1 (prospectively ascertained) and Cohort 2 (retrospectively ascertained): Cases of probable or confirmed myocarditis/pericarditis associated with COMIRNATY

- 1. Age <21 years
- 2. Presentation to a participating medical center with evaluation in Emergency Room and/or hospitalization
- Received either the 1st, 2nd, 3rd, or booster dose(s) of COMIRNATY ≤21
  days of symptom onset, even if a different brand of COVID-19 vaccine had
  been administered in earlier vaccinations. Participants can be retrospectively

[figure not shown]
- ascertained and enrolled at any time from their COMIRNATY-associated myocarditis/pericarditis.
- 4. Probable or confirmed myocarditis/pericarditis as per the contemporaneous CDC case definition (Table 3)\*11-12 at the time of diagnosis.
- 5. Capable of giving signed informed consent/assent (by parents/legal guardians of minors and/or patients) as described in (see protocol), which includes compliance with the requirements and restrictions listed in the Informed Consent/Assent Document and in this protocol OR meets criteria for waiver of consent.

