## **Acute Pericarditis Probable Case** • Presence of $\geq 2$ new or worsening of the following clinical features: acute chest pain pericarditis rub on exam new ST-elevation or PR-depression on ECG new or worsening pericardial effusion on echocardiogram or MRI · Autopsy cases may be classified as pericarditis on basis of meeting histopathologic criteria of the pericardium

Adapted from Centers for Disease Control and Prevention. Copyright ©2021, Centers for Disease Control and Prevention.

Abbreviations: cMRI = cardiac magnetic resonance imaging; ECG = electrocardiogram.

\* Persons who lack the listed symptoms but who meet other criteria may be classified as subclinical myocarditis (probable or confirmed).

- † Using the Dallas criteria. Autopsy cases may be classified as confirmed clinical myocarditis on the basis of meeting histopathologic criteria if no other identifiable cause. § To meet the ECG or rhythm monitoring criterion, a probable case must include at least one of 1) ST-segment or T-wave abnormalities; 2) Paroxysmal or sustained atrial, supraventricular, or ventricular arrhythmias; or 3) AV nodal conduction delays or intraventricular conduction defects, excluding first degree AV block, Mobitz Type I (Wenkebach), and incomplete right bundle branch block.
- ¶ Using either the original or the revised Lake Louise criteria.

  †† Typically described as pain made worse by lying down, deep inspiration, or cough, and relieved by sitting up or leaning forward, although other types of chest pain might occur.

\*This table is adapted from Bozkurt et al (2021) and the Centers for Disease Control and Prevention. 11-14

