## **Table 4. Study Variables**

Variable	Role	Data	Operational definition
		source(s)	
Medical history: Date of admission, intensive care unit (ICU) stay, comorbid conditions including overweight and obesity by BMI (age-and sex-adjusted z scores using CDC [primary] and World Health Organization [WHO] [secondary] norms), prior doses and brands of COVID-19 vaccine administered before the COMIRNATY vaccine given within 7 days of myocarditis/pericarditis onset, prior history of myocarditis/pericarditis, clinical features at the time of presentation (e.g., chest pain, fever); type of shock if present (hypovolemic, distributive, cardiogenic); individual organ dysfunction at presentation; mechanical ventilation (date of intubation and first extubation, total days of intubation); ECMO, other serious medical events, death, discharge date.	Predictors	Medical records; participant report	All study participants: post-vaccine* (Cohorts 1 and 2) and control (Cohort 3) participants
Treatments for myocarditis/pericarditis or myopericarditis: Anti-inflammatory agents [e.g., intravenous immunoglobulins (IVIG), steroids, colchicine]; symptomatic treatments and analgesics [e.g., non-steroidal anti- inflammatory drugs (NSAIDs)]; antithrombotic (anticoagulants, antiplatelet agents), pressors, vasoactive agents, heart failure therapies [digoxin, diuretics, angiotensin converting enzyme (ACE) inhibitors, angiotensin II receptor blockers (ARBs), and procedural treatments (i.e., pacemaker, implantable cardiac defibrillator, mechanical circulatory support and heart transplantation].	Predictors	Medical records	All study participants: post-vaccine* (Cohorts 1 and 2) and control (Cohort 3) participants
Clinical Labs: Troponin	Predictors	Medical records	Per protocol, in post-vaccine* myocarditis/pericarditis (Cohorts 1 and 2): daily troponins (I or T in accordance with routine center clinical practice) while participants are

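### Section 9.9 says every participant is symptomatic with clinical disease, but Cohort 3 entry requires no cardiac symptom, so the objective 2 comparison may mix symptom thresholds

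*Protocol*

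**What the plan says.** Three parts of the protocol bear on this.

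- **Section 9.9 (limitations).** It states "The COMIRNATY myocarditis and comparison participants are symptomatic" patients diagnosed in medical centers, adds that the study "population will only include those with clinical myocarditis/pericarditis", and concludes that "results from this study cannot be generalized to those in a subclinical" population.
- **Section 9.2.1 (entry).** "Patients must meet all of the following inclusion criteria to be eligible for inclusion in the study". Criterion 4, in the vaccine cohorts and in Cohort 3, is "Probable or confirmed myocarditis/pericarditis as per the contemporaneous CDC case definition", with a pointer to Table 3. A footnote to that table reads: "Persons who lack the listed symptoms but who meet other criteria may be classified as subclinical myocarditis (probable or confirmed". For Cohort 3, criterion 4 is also spelled out in the text. A probable case needs at least one new troponin, ECG/rhythm, echocardiographic or cMRI finding. A confirmed case needs histology, or raised troponin together with cMRI findings.
- **Table 4 (variables).** Medical history includes "clinical features at the time of presentation (e.g., chest pain, fever"), for all three cohorts. The table's footnote defines the post-vaccine cohorts by a COMIRNATY dose no more than 21 days from the start of myocarditis symptoms.

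**The concern.** Section 9.9 describes the enrolled population as a fact and rests a conclusion on it. A study report that repeats it would tell readers that vaccine and comparator cases were both recognised through clinical cardiac disease. If the comparator can be entered on a laboratory or imaging finding alone, that assurance is not backed by the criteria.

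What is at stake is secondary objective 2, which compares acute and long-term cardiac outcomes between COMIRNATY-associated and COVID-19-associated disease. If cases without cardiac symptoms have fewer sequelae, and they enter only or mainly through Cohort 3, the comparator rate falls and the contrast moves against the vaccine cohorts for a reason unrelated to cause of disease. Section 9.9 does list ways in which the comparator differs (less acute cMRI, and a different mix of race, ethnicity, sex and age). Symptom threshold is not among them.

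**Working it through.** The question is one of eligibility text, so the check is to follow a patient without cardiac symptoms through each cohort's criteria.

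**Cohorts 1 and 2**
1. Criterion 2 requires emergency room evaluation and/or hospitalization.
2. Criterion 3 times the COMIRNATY dose against symptom onset, with a 21-day limit. A patient with no symptoms has no onset date and fails it.
3. The Table 4 footnote makes clear that the symptoms meant are those of myocarditis.
4. Criterion 4 alone would let in a subclinical case through the Table 3 footnote, but the criteria apply jointly, so steps 2 and 3 largely close that route. A narrow gap remains: criterion 3 does not say that the symptom must be one listed in Table 3.

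**Cohort 3**
1. Criterion 2 again requires emergency room or hospital evaluation.
2. Criterion 3 requires symptomatic, test-positive COVID-19 or MIS-C by the CDC definition. Neither branch, as written here, asks for a cardiac symptom, and there is no date of onset for myocarditis.
3. Criterion 4 is met for a probable case by one new test finding and for a confirmed case by histology or by troponin plus cMRI. No cardiac symptom is listed.
4. The Section 9.2.2 exclusions cover alternative etiology, pre-existing cardiac conditions and recent investigational products. None removes subclinical disease.
5. So a patient with MIS-C, a raised troponin and no cardiac symptom meets every disease criterion.

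**Result**

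| | Cardiac symptoms needed for entry? | Section 9.9 |
|---|---|---|
| Cohorts 1 and 2 | In effect yes (criterion 3, Table 4 footnote) | Clinical cases only |
| Cohort 3 | No | Clinical cases only |

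**Size.** The documents give neither the share of Cohort 3 without cardiac symptoms nor outcome rates by symptom status. As an illustration only, let *f* be that share, and let the 6-month composite be *r₁* in symptomatic and *r₂* in other cases. The Cohort 3 rate falls below *r₁* by *f* × (*r₁* − *r₂*). All inputs here are assumed, with *r₁* = 15%:
- *f* = 10%, *r₂* = 8%: 0.10 × (0.15 − 0.08) = 0.007, giving 14.3%.
- *f* = 30%, *r₂* = 3%: 0.30 × (0.15 − 0.03) = 0.036, giving 11.4%.

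Under these assumptions the contrast moves by 0.7 to 3.6 percentage points. With other inputs it could be negligible or larger.

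**The case against.** The best defence is that Section 9.9 contrasts hospital-diagnosed patients with undetected disease in the community. In that sense Cohort 3 patients are symptomatic: they have COVID-19 or MIS-C and came to an emergency room or hospital. The Table 3 footnote is also permissive, is carried over from an adapted CDC table and speaks of myocarditis only. The myocarditis rows of that table could not be read in the text examined, so the footnote's anchor is unconfirmed. Finally, analysis flags and sensitivity analyses normally belong in the SAP.

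Much of this stands, and it rules out three stronger readings that a reader might infer.

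- *That the primary sequelae rate is diluted by subclinical cases.* The primary objective concerns COMIRNATY cases, where criterion 3 and the Table 4 footnote in effect require myocarditis symptoms. Dilution there is not shown.
- *That the caution about generalisation is wrong.* It is a conservative disclaimer. A few hospital-evaluated cases without cardiac symptoms would not make the results applicable to subclinical disease in the community.
- *That subclinical cases have been enrolled.* The text shows that they are eligible for Cohort 3, not that any are in it.

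The defence does not rescue the sentence that only clinical myocarditis/pericarditis is included. Symptoms of COVID-19 or MIS-C are not symptoms of myocarditis, and Cohort 3 criterion 4 shows this without relying on the Table 3 footnote. Nor is this a matter for the SAP: the protocol contradicts itself on who is in the study.

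**Conclusion.** The point holds for Cohort 3 and for secondary objective 2. Section 9.9 asserts a restriction to clinical, symptomatic disease that the comparator's entry criteria do not impose. Since the vaccine cohorts in effect do impose it, the two sides of the comparison can differ in symptom threshold.

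The primary objective is little affected, and nothing here calls for a change to its analysis set. The effect on objective 2 cannot be sized from the documents. Its direction, a lower comparator rate, rests on the assumption that cases without cardiac symptoms have fewer sequelae. Whether it matters depends on how many of the planned 100 Cohort 3 participants had no cardiac symptom at presentation, which the collected data should show.

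**What to change.** 1. Reconcile Section 9.9 with the Table 3 footnote and Cohort 3 criterion 4: state that Cohort 3 may include cases without cardiac symptoms, and add symptom threshold to the listed differences between comparator and vaccine cohorts. The caution against generalising to community subclinical disease can stay.
2. Derive a yes/no flag for myocarditis symptoms at presentation from the Table 4 medical history data, and report its count in each cohort.
3. Present the objective 2 comparisons for all cases and, as a sensitivity analysis, for symptomatic cases only.
4. Leave the primary analysis set unchanged.

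The cost is a wording change, one derived variable and one extra table, with no new data collection. The drawback is a smaller Cohort 3 in the sensitivity comparison: under the assumed 10% to 30% share, 90 down to 70 of the planned 100.

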## 9.10. Other Aspects

Not Applicable

### 10. PROTECTION OF HUMAN PARTICIPANTS

## 10.1. Patient Information

This study involves data that exist in de-identified/anonymized structured format and contain no patient personal information.

## 10.2. Patient Consent

As this study involves deidentified/anonymized structured data, which according to applicable legal requirements do not contain data subject to privacy laws, obtaining informed consent from patients by Pfizer is not required.

## 10.3. Institutional Review Board (IRB)/ Ethics Committee (EC)

Under C4591036, a central IRB with reliance from local IRBs (or local IRB if not applicable) is responsible for the safe conduct of research at each study site. C4591036 also uses the Pediatric Heart Network Data and Safety Monitoring Board (DSMB). The DSMB is independent of the study team and includes only external members. The board is responsible for ongoing monitoring of the safety of participants in the study according to the DSMB Charter. The recommendations made by the DSMB to alter the conduct of the study are forwarded to Pfizer personnel for final decision. Pfizer will forward such decisions, which

may include summaries of aggregate analyses of endpoint events and of safety data that are not endpoints, to regulatory authorities, as appropriate.

This study will also be reviewed by a central IRB. A copy of the approval will be forwarded to Pfizer.

## 10.4. Ethical Conduct of the Study

The study will be conducted in accordance with legal and regulatory requirements, as well as with scientific purpose, value, and rigor and follow generally accepted research practices described in Guidelines for Good Pharmacoepidemiology Practices (GPP).

### 11. MANAGEMENT AND REPORTING OF ADVERSE EVENTS/ADVERSE REACTIONS

This study involves data that exist as structured data by the time of study start or a combination of existing structured data and unstructured data, which will be converted to structured form during the implementation of the protocol solely by a computer using automated/algorithmic methods, such as natural language processing. In these data sources, individual patient data are not retrieved or validated, and it is not possible to link (i.e., identify a potential association between) a particular product and medical event for any individual. Thus, the minimum criteria for reporting an adverse event (AE) (i.e., identifiable patient, identifiable reporter, a suspect product, and event) cannot be met.

### 12. PLANS FOR DISSEMINATING AND COMMUNICATING STUDY RESULTS

As per EMA Guideline on good pharmacovigilance practices (GVP) – Module VIII (Rev 3) the study and its protocol will be registered in the HMA-EMA Catalogues of real-world data sources prior to the start of data collection. Any publication of the results from this study will follow The International Committee of Medical Journals Editors (ICMJE) Recommendations for the Conduct, Reporting, Editing, and Publication of Scholarly Work in Medical Journals. In the event of any prohibition or restriction imposed (e.g., clinical hold) by an applicable competent authority in any area of the world, or if Carelon (CRO for studies C4591036 and C4591079) is aware of any new information which might influence the evaluation of the benefits and risks of a Pfizer product, Pfizer should be informed immediately.

**ANNEX 1. LIST OF STANDALONE DOCUMENTS** 

None

**ANNEX 2. ENCEPP CHECKLIST FOR STUDY PROTOCOLS** 

N/A

**ANNEX 3. ADDITIONAL INFORMATION** 

None

